8.1.4 Electrocardiogram

Computerised single 12-lead ECG recordings will have to be obtained locally according to Table 1. Each lead shall be recorded for at least 3 beats at a speed of 25 mm/s.

The following parameters will be recorded: ventricular rate, PR interval, QRS duration, QT interval and QTcF. These parameters plus the judgement by the physician will be entered in the eCRF. Print-outs of ECGs will have to be signed, dated and filed at the site.

At baseline, the Investigator must document clinically relevant ECG findings on the appropriate baseline eCRF pages and in the subject's hospital records. Any new clinically relevant ECG finding or aggravation/worsening of an already existing finding as assessed by the Investigator, must be reported as an AE (see Section 10).

[figure not shown]
8.1.5 **Body Height, Weight**

Body height (in cm, without shoes) must be measured at the screening visit only. Body weight must be measured in underwear or light clothing without shoes. The same calibrated scale must be used throughout the trial. Any new clinically relevant change in body weight must be reported as an AE (see Section 10).

8.1.6 **Documentation of Concomitant Treatments**

All medications and treatments prescribed at the moment of informed consent must be documented on the appropriate eCRF pages. In addition, treatments prescribed up to at least 3 months prior to obtaining the informed consent must be documented on the appropriate eCRF pages, irrespective if the treatment is still ongoing at the time of screening. All changes to or addition of concomitant treatments as of informed consent must be recorded (including changes in dose, change in formulation, starting or stopping medications) in the

eCRF. If the indication for changing a subject's concomitant treatment constitutes a new medical condition or a worsening of an existing clinical condition which is considered by the Investigator as being clinically relevant, the indication must be documented as an AE (see Section 10).

8.1.9 Local Laboratory Parameters

The laboratory tests to be assessed and analysed locally according to Table 1 results will be transferred into the eCRF.

8.1.9.1 Haemoglobin

Hb levels to be assessed locally at each study visit V3 to Visit V8.

8.1.9.2 Urine Tests

- Urine pregnancy test: human chorionic gonadotropin for females of childbearing potential to be assessed at baseline and study visits V3-V8.
- Urinalysis: pH, protein, glucose, ketone, blood, spot urine for assessment of protein/creatinine and albumin/creatinine ratio (may be done centrally).
- Urine drug screening: alcohol, amphetamines, cannabinoids, cocaine, opioids, phencyclidine.

8.1.10 Central Laboratory Parameters

Details concerning the central blood samples collection, blood withdrawal, processing and storage will be provided in a Laboratory instruction manual. The following Laboratory parameters will be assessed during the study according to Table 1.

Although the assessments should preferably be performed centrally, due to COVID-19 pandemic, assessment may be performed in a local laboratory at site or at a laboratory near to subject's home in case shipment of samples to the central laboratory is no longer

possible. This would notably concern key safety laboratory parameters which should at minimum include haematology panel (RBC, Hb, haematocrit, mean corpuscular volume, mean corpuscular Hb, mean corpuscular Hb concentration, white blood cell count with differential, platelets count), coagulation (prothrombin time, activated partial thromboplastin time, thrombin time) and liver function tests (ALT, AST, GGT total bilirubin, alkaline phosphatase).

8.1.10.1 Haematology, Biochemistry, Blood Clotting and Serology

- Electrolyte status (sodium, potassium, magnesium, calcium, chloride), total bilirubin, urea, uric acid, creatinine, total protein, alkaline phosphatase, AST, ALT, GGT, glutamate dehydrogenase, LDH, haptoglobin, amylase, bicarbonate, eGFR, unconjugated bilirubin, creatine phosphokinase, folic acid, Vitamin B₁₂, albumin, glucose, total cholesterol, and triglycerides. Total serum iron, serum ferritin, unsaturated iron binding capacity, calculated TSAT (screening visit only).
- Prothrombin time, activated partial thromboplastin time, thrombin time.
- Beta-human chorionic gonadotropin in serum.
- HIV 1/2 antibodies, HCV antibodies and RNA, HBsAg, hepatitis B core antibodies and optional HBV DNA.

8.1.10.2 PD Iron

- PD iron: Total serum iron, serum ferritin, serum transferrin, unsaturated iron binding capacity, calculated TSAT,
- •
- Biomarker/genotyping.

In subjects consenting for additional biomarker samples and genotyping, blood samples will be taken. The baseline biomarker blood sample will be drawn prior to the first administration of study treatment. Blood samples will be stored for up to 3 years after the end of the trial for future analyses of biomarkers of scientific interest. Details concerning the blood samples storage will be provided in an instruction manual and results of these exploratory analyses will be not part of the clinical study report of the main study.

8.1.10.3 Pharmacokinetics

Blood samples for the determination of VIT-2763 plasma concentrations (sparse sampling) are collected on Visit 3 and Visit 7 at pre-dose trough and at approximately 1 hour and 4 hours post-dose, and on Visits 6 and 8 at pre-dose trough and approximately at 1 hour and 3 hours post-dose.

8.1.11 Blood Volumes Drawn for Each Subject

The approximate total volume of blood drawn during the study for each subject is shown in Table 3.

Approximate Blood Volumes Drawn for Each Subject in the Study Table 3

Visit	Screen V1	Screen V2 (Optional)	Baseline V3	V4	VS	9/	77	8/	
Study Day	-28	-15	1	7	14	28	99	84	
Visit Window (±d)	N/A	±3	N/A	1	∓ 5	#3	∓3	∓3	
Laboratory sample									Total (ml)
Haematology	×	ı	×	ı	×	×	×	X	
Biochemistry	×	ı	×	1	×	×	×	X	
Coagulation	×	I	×	ı	I	×	ı	X	
Biomarker/genotyping ⁽¹⁾	ı	I	×	1	I	ı	ı	X	
Pregnancy test	$\mathbf{X}^{(2)}$	I	ı	1	I	ı	ı	$X^{(2)}$	
Serology ⁽³⁾	$X^{(3)}$	I	I	ı	I	ı	ı	ı	
VIT-2763 PK ⁽⁴⁾	I	I	х3			x 3	x3	x3	
Hb local ⁽⁵⁾	ı	×	×	×	×	×	×	X	
PD iron	ΙΙ	ΙΙ	×	×	×	×	×	×	
Approximate total volume (ml) per visit (adults)	30	3	22	30	34	42	44	52	292 ml
Approximate total volume (ml) per visit (adolescents)	26	3	52	24	29	36	40	52	262 ml
Taken in subjects consenting to genotyping/biomarker sampling. For women only. Samples will be derived from serum biochemistry tube. Including HCV RNA and HBV DNA. Programme of the service of the service does trough and amountain to 1 hours of 1 h	houre to A house	and door							
4 Fr. Samples will be conceded on viais 3 to 8 at pre-tose trough and approximately up to 1 nour to 4 nous post-tose. 5 Local haematology sample to assess Hb will be taken locally at study site and results must be available at day of dosing (sample at optional Visit V2) 6	be available at d	post-dosc. av of dosing (sample at o	ntional Visit V2)						

will be assessed centrally. Samples will be collected on Visits 3 to 8 7 PD measurements including serum iron, serum territin, serum transferrin, unsaturated iron binding capacity, calculated TSAT, approximately 2 hours post-dose.

8 Approximately 2 hours post-dose.

N/A=Not applicable;

Ferroportin Protocol No. VIT-2763-THAL-201 12 April 2021

PD=Pharmacodynamics; PK=Pharmacokinetics;

8.2 End of Treatment (or Early Discontinuation) Procedures

A visit will take place on completion of the treatment or early discontinuation/withdrawal (i.e., at Week 12 (Visit 8)). All assessments should be performed as detailed in Table 1 end of treatment, V8.

Visit window for end of treatment visit is ± 3 days.

8.3 Safety Follow-up (EOS) Procedures

All subjects, whether completing the treatment or who have withdrawn prematurely, will be followed up 4 weeks (28 days) after their last administration of study treatment to collect any new AEs and concomitant medications (i.e., at Week 16 (Visit 9)). This visit may be conducted by telephone call or as an in-clinic visit. If the Investigator has not seen the subject at a clinic at the end of the reporting period, the Investigator must attempt 3 telephone calls to the subject, and if there is no response, the source documents and the eCRF should document the reason for study discontinuation as "lost to follow-up".

9. STUDY ASSESSMENTS

9.1 **Description of Study Assessments**

9.1.1 **Screening Visit**

9.1.1.1 Screening Visit V1 Days -28 to Day -1 – Performed In-hospital

- Subjects who have a documented diagnosis of β -thalassaemia will be screened within 4 weeks prior to the baseline/randomisation visit to determine potential eligibility to participate in the VIT-2763-THAL-201 trial.
- The Investigator will obtain written informed consent from potentially eligible subjects before any trial related procedure is performed. In case of extraordinary events (e.g., COVID-19 pandemic) it is acceptable to have the informed consent via e-mail, SMS or a verbal consent (a witness is required) if allowed per local country guidance. Written consent has to be provided as soon as possible and must be properly recorded in the source documentation.
- Protocol required procedures according to Table 1, including medical/medication history, physical examination, weight and height, vital signs.
- As of the date of informed consent for each subject, the sites will document in the eCRF all AEs and changes/additions made to concomitant medications. SAEs will be reported as they occur but no later than 24 hours after the Investigator's awareness of the event.
- Subject demographics and baseline characteristics will be assessed.
- A single 12-lead ECG will be conducted.
- A blood test will be drawn, which will be analysed centrally, to determine if the subject is eligible according to the main inclusion and exclusion criteria and Table 1.
- Urine will be taken for urinalysis (pH, protein, glucose, ketone, blood, spot urine for assessment of protein/creatinine and albumin/creatinine ratio) and urine drug and alcohol screen.
- During the same blood draw, a serum pregnancy test will be taken for female subjects of childbearing potential.
- A serology test will be conducted to determine HBsAg, HBV, HCV, and HIV.

9.1.1.2 Screening Visit V2 (Day -15±3 Days) - Performed In-hospital - Optional

If subjects did fulfil the main inclusion criteria and did not meet any exclusion criteria observed at Visit V1, they will be asked to attend a second screening Visit V2 in order to determine the Hb level. Note: If there is 1 retrospective Hb value available from the subject at maximum of 2 weeks prior to screening (Day -28), the Hb value can be taken into consideration in order to verify if the inclusion criterion is met (mean baseline Hb \leq 11 g/dl, \geq 2 consecutive measurements \geq 1 week apart within 6 weeks prior to randomisation). If obtained Hb values show more than 10% relative difference and more than 1.0 g/dl absolute change between the highest and lowest value, the subject must be excluded.

[figure not shown]
- In addition, other eligibility criteria including changes in AEs and changes/additions
 made to concomitant medications will be re-assessed and it will be determined whether
 the subjects are still eligible.
- In case there is no retrospective Hb value, it is allowed to schedule an optional screening Visit V2 and baseline V3 the same day providing that local Hb result can be obtained on the day of combined V2/V3 visit and that there should be at least 1 week between screening Visit V1 and the combined V2/V3 visit. If V2 and V3 are done the same day, site should only complete V3 in EDC.

9.1.2 Baseline Visit V3 (Day 1) – Performed In-hospital

To accommodate local hospital practice, the subject may attend the V3 visit either at the day of the first dose of study treatment, or the day before the planned randomisation day. Note that a planned overnight stay prior study treatment administration does not fulfil the criteria of an SAE unless there is a medical reason for doing this.

- If subjects did fulfil the main inclusion criteria and did not met the exclusion criteria observed from the Visit V1 and optional V2, they will be asked to attend baseline Visit V3. The Investigator will perform/complete the baseline procedures/assessments as shown in Table 1.
- Eligibility criteria including changes in the medical history, AEs and changes/additions made to concomitant medications will be re-assessed and it will be determined whether the subject is still eligible.
- Physical examination will be done and vital signs will be checked.
- 12-lead ECG.
- Determination of Hb level will be processed locally. Subjects must have a mean baseline Hb ≤11 g/dl, based on at least 2 consecutive measurements ≥1 week apart within 6 weeks prior to randomisation/baseline. If obtained Hb values show more than 10% relative difference and more than 1.0 g/dl absolute change between the highest and lowest value, the subject must be excluded. Note: If there is 1 retrospective Hb value available for the subject at maximum of 2 weeks prior to screening (Day -28), the Hb value can be taken into consideration. A subject not meeting this criterion would be excluded but can be rescreened at maximum 2 times at a later time point.

- In addition, for females of childbearing potential, the urine pregnancy test must be negative.
- Further baseline laboratory blood draws will be taken according to Table 1:
 - Baseline PK sample for determination of VIT-2763 concentrations.
 - Blood draws for haematology, biochemistry, coagulation.
 - PD iron,
 - Genotyping/biomarker sampling in subjects consented.
 - Urine will be taken for urinalysis (pH, protein, glucose, ketone, blood, spot urine for assessment of protein/creatinine and albumin/creatinine ratio).

9.1.3 Randomisation and Administration of the First Dose of Study Treatment

- Upon completion of the baseline visit procedures/assessments eligible subjects will be randomised using a validated centralised procedure (IWRS) to receive VIT-2763 or placebo according to the randomisation scheme (Cohort I and II).
- Subjects eligible for randomisation will receive a randomisation number. Randomised subjects who terminate their study participation for any reason regardless of whether the study drug was taken or not, will retain their randomisation number. The next subject will be given the next randomisation number.
- The assignment of subjects to either active treatment dose or matching placebo will be based on body weight at screening, according to Section 6.4.

[figure not shown]
- The first dose of study treatment must be administered on the same day as randomisation.
- The medication (VIT-2763 or placebo) will be administered in the morning in conjunction with water approximately 1 hour after meals between approximately 08:00 a.m. and 10:00 a.m. in the morning. Subjects are asked to stay in the hospital until up to 4 hours at selected visits for PK sampling. At 2-3 hours post study drug administration a 12-lead ECG will be conducted. To maintain the BID dosing schedule, i.e., after having received a dose in the morning at the hospital, the subjects will be advised in taking the study medication in the evening approximately 1 hour apart from meals and with water at approximately the same clock time each day (between 08:00 p.m. and 10:00 p.m. in the evening).

Study medication will be given to the subject to administer at home until the next visit.

9.1.4 Post-randomisation Visits V4 (Week 1) to V8 (Week 12 or Early Discontinuation)

- Subjects will return to the out-patient clinic at 1 (±1 day), 2 (±2 days), 4 (±3 days), 8 (±3 days) and 12 weeks (±3 days) after randomisation.
- If a subject cannot return to the site for a study visit due to COVID-19 pandemic, the Investigator will conduct a remote visit (e.g., telemedicine, phone call), a visit at the subject's home, or in facilities near to the subject's home to evaluate subject safety and eligibility to continue the study therapy, if applicable and as per local country guidance.
- At the remote/home visits the Investigator should at minimum perform the following: evaluation of the subject's general condition, collection of information on any new and ongoing adverse events, collection of information on the IMP intake and concomitant medications use. Scheduled urine samples may be collected at a home visit, or in laboratories near to the subject's home and should be processed locally. Scheduled blood samples may also be collected at home visit or laboratories near to the subject's home and sent to the central laboratory if possible, otherwise processed locally. Safety analyses such as haematology panel (RBC, Hb, haematocrit, mean corpuscular volume, mean corpuscular Hb, mean corpuscular Hb concentration, white blood cell count with differential, platelets count), coagulation (prothrombin time, activated partial thromboplastin time, thrombin time) and liver function tests (ALT, AST, GGT, total bilirubin, alkaline phosphatase) should be done at the minimum.
- Subjects will have to come in the morning of the visit before taking the study medication, and have to come on an empty stomach. Drinking of water ad libitum is allowed. If a subject is not able to visit the site for IMP resupply due to COVID-19 pandemic, a direct shipment of the study drug to the patient home/place of stay can be implemented, if allowed by the local regulations. The shipment will be performed by a logistics provider in a traceable and temperature-controlled manner.

- During the out-patient visits, the Investigator will check the vital signs (including weight at V8 only), also for AEs, check concomitant medication. On Visit 8 also a physical examination will be done.
- At Week 1 (Visit 4), Week 2 (Visit 5), Week 4 (Visit 6), Week 8 (Visit 7) and Week 12 (Visit 8), a blood test to assess Hb will be performed and analysed locally. The Hb value needs to be available at the day of dosing before the subject is leaving the hospital, and will be documented in the eCRF. In addition, a urine pregnancy test will be drawn.
- Urine will be taken for urine pregnancy and test urinalysis (pH, protein, glucose, ketone, blood, spot urine for assessment of protein/creatinine and albumin/creatinine ratio), blood samples for haematology and clinical chemistry (all visits) and coagulation (Visits 6 and 8).
- Dosing will only be done in subjects for whom the urine pregnancy test is negative in females of childbearing potential. In case of a Grade 4 including Hb <8.0 g/dl (5.0 mmol/l) for female subjects or <8.5 g/dl (5.3 mmol/l) for male subjects, and with an absolute Hb drop from baseline >2 g/dl for males and females, and confirmed by subsequent repeat ≥24 hours apart, study drug will not be re-dispensed.
- Subjects will bring back the study medication dispensed to them at the previous visit
 and returned drug will be documented. Subjects will be dispensed new study drug and
 will take the first morning dose in the hospital as described in the 'Treatment' section.
 Approximately 2-3 hours after dosing a 12-lead ECG will be done, blood will be taken
 for PK (selected visits) and PD measurements (all visits),
- In subjects that have consented for genotyping and biomarker sampling an additional blood sample will be taken on Visit 8 only.

If subject withdraws prematurely, all assessments at V8 should be performed, if possible.

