- Upon completion of the baseline visit procedures/assessments, eligible subjects will be randomised using a validated centralised procedure (IWRS) to receive VIT-2763 or placebo according to the randomisation scheme (Cohort I and II).
- The first dose of study treatment must be administered on the same day as randomisation.

[figure not shown]
• The medication (VIT-2763 or placebo) will be administered in the morning in conjunction with water approximately 1 hour apart from meals between 08:00 to 10:00 a.m. Subjects are asked to stay in the hospital until up to 4 hours post administration at selected visits. To maintain the BID dosing schedule, i.e., after having received a dose in the morning at the hospital, the subjects will be advised in taking the study medication in the evening approximately 1 hour apart from meals and with water at approximately the same clock time each day between 8:00 p.m. and 10:00 p.m. in the evening. Subjects will receive study medication for home intake until the next visit.

Visits V4 to V8 (or Early Discontinuation)

- Subjects will return to the out-patient clinic at 1 (±1 day), 2 (±2 days), 4 (±3 days), 8 (±3 days) and 12 weeks (±3 days) after randomisation.
- If a subject cannot return to the site for a study visit due to COVID-19
 pandemic, the Investigator will conduct a remote visit (e.g., telemedicine,
 phone call), a visit at the subject's home, or in facilities near to the subjects'
 home to evaluate subject safety and eligibility to continue the study therapy,
 if applicable and as per local country guidance.
- During the out-patient clinic visits, the Investigator will perform the procedures/assessments as shown in Table 1 for the respective visit.
- •
- At Weeks 1 (Visit 4), 2 (Visit 5), 4 (Visit 6), 8 (Visit 7) and 12 (Visit 8) an
 additional blood test will be performed and analysed locally for the
 assessment of Hb levels and will be documented in the eCRF. In addition, a
 urine pregnancy test will be drawn.
- For female subjects of childbearing potential, dosing will only be done for whom the urine pregnancy test is negative.
- After procedures/assessments are performed, the morning dose (VIT-2763 or placebo) will be administered in conjunction with water approximately 1 hour after meals between 08:00 to 10:00 a.m.

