### 5.7.2 Clinical Laboratory Evaluations

A list of all protocol specified clinical laboratory tests are given in Appendix A and will be performed at screening, baseline, week 1, week 2, week 4, week 8 and week 12 for haematology, biochemistry and urinalysis and at screening, baseline, week 4 and week 12 for coagulation in accordance with the Schedule of Events in section 2.3. For analyses, Planned Assessment Windows (see Section 2.2.3) are defined for each visit.

Descriptive statistics will be performed for laboratory parameters on a continuous scale for the scores and change from baseline for each visit split by treatment group.

If multiple tests were performed at baseline, the latest non-missing measurement prior to the first administration of study treatment will be used for the baseline value. For multiple tests at post-baseline visits occurring during the same visit window, the closest measurement will be used for the analyses and summary tables. When two measurements are exactly equidistant to the exact visit date, the later will be used for the analyses and summary tables. Laboratory values expressed as 'less than" or "greater than" will be imputed using the next numerical value (i.e. '<2.00' imputed as 1.99, ">0.3" imputed as 0.4).

Shift tables for the haematology and biochemistry laboratory parameters comparing values low, normal and high using the standard reference ranges will be presented for the baseline laboratory measurement versus the endpoint measurement for each subject. The number and percentage of subjects with abnormal values for each analyte will be summarized at each analysis visit. Abnormal values for each analyte will be determined using normal ranges provided by the central laboratory. The descriptive analysis by visit will also include an overall summary. If any of the subject's post-baseline measurements are abnormal (low or high), then the subject is classified as abnormal in the overall summary.

All laboratory results (local and central values) will be listed, including all unscheduled visits.

Only central laboratory parameters will be analysed.

eGFR formula: 186 x (Creatinine/88.4)-1.154 x (Age)-0.203 x (0.742 if female) x (1.210 if black)

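### An empty-stomach condition is set for V4 to V8 only, so within-arm changes from baseline in glucose and triglycerides can include a change in feeding state

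*Protocol*

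**What the plan says.** - **V4 to V8.** Protocol 9.1.4: "Subjects will have to come in the morning of the visit before taking the study medication, and have to come on an empty stomach". Water is allowed. The same section asks for haematology and clinical chemistry at every one of these visits, without a clock time or a time since the last meal.
- **V1.** Protocol 9.1.1.1 says only: "A blood test will be drawn, which will be analysed centrally, to determine if the subject is eligible". No feeding condition is attached.
- **V3.** Protocol 9.1.2: "Further baseline laboratory blood draws will be taken according to Table 1". Again there is no feeding condition. The visit may be held on the dosing day or on the day before randomisation.
- **Dosing and meals.** At V3 the dose is due "approximately 1 hour after meals between approximately 08:00 a.m. and 10:00 a.m. in the morning" (Protocol 9.1.3). The Synopsis for V4 to V8 says: "After procedures/assessments are performed, the morning dose (VIT-2763 or placebo) will be administered in conjunction with water approximately 1 hour after meals". Protocol 6.4.2.1 and 6.4.2.2 give the same meal rule for active drug and placebo on all dosing days.
- **Baseline.** For laboratory tests in general, SAP 5.7.2 says that "the latest non-missing measurement prior to the first administration of study treatment will be used for the baseline value". SAP 5.1.2 makes exceptions for the iron markers.
- **Analytes.** Glucose, total cholesterol and triglycerides are in the safety panel (Protocol 8.1.10.1). Changes in laboratory safety tests are part of the primary endpoint (Protocol 3.4.1).

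**The concern.** Glucose and triglycerides depend on when the subject last ate. If the baseline sample may be fed and the on-treatment samples come from subjects told to arrive on an empty stomach, the change from baseline contains the drug effect plus any change in feeding state. The planned output is descriptive: values, changes and shift tables by arm, with no between-arm estimate (Protocol 12.1, SAP 3.2 and 5.7.2). A reader who takes an active-arm change at face value could mistake a sampling artefact for a treatment effect.

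A second difficulty is that the visit-day instructions for V4 to V8 call for arrival on an empty stomach and also for a dose about an hour after a meal, yet no meal at the site is described. The PK samples, the 2-3 hour ECG and the 2-hour iron sample all follow that dose.

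**Working it through.** The plan states no figure on this point, so there is none to reproduce. The check sets the passages side by side and then works out what a common shift does to each summary.

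**1. Feeding state by sample**

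| Sample | Feeding state in the text | Role in the SAP |
|---|---|---|
| V1 chemistry | Not set | Baseline for serum iron, ferritin, UIBC and TSAT; fallback baseline for glucose and triglycerides |
| V3 chemistry | Not set | Usual baseline for glucose and triglycerides |
| V4 to V8 chemistry | Empty stomach on arrival; draw time not set | On-treatment values |
| V3 to V8 iron markers | About 2 h post-dose; feeding state not set | On-treatment values; V3 is also the transferrin baseline (SAP 5.1.2, 5.1.3) |

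The asymmetry is therefore documented for safety chemistry. It is not documented for iron. If the meal rule for dosing is followed, the iron sample falls about 1 h + 2 h = 3 h after eating, and this holds at V3 and at V4 to V8 alike.

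**2. Effect on the summaries**

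Let *d* be the drug effect, *s* the shift in a subject who was fed at baseline and fasting on treatment, and *p* the share fed at baseline. Other time effects are left aside.

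- Expected change, active arm: *d* + *p·s*
- Expected change, placebo arm: *p·s*
- Expected difference, active minus placebo: *d*

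With *p* assumed between 0.10 and 0.75, the within-arm artefact is 0.10*s* to 0.75*s*. The documents give no value for *p* or *s*.

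**3. Chance imbalance**

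At the planned minimum of 20 adults allocated 8:8:4 (Protocol 12.3), placebo has 4. The SD of the chance difference between two arms in the share fed at baseline is √[*p*(1−*p*)(1/n₁ + 1/n₂)].

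| Assumed *p* | One active arm v placebo (8 v 4) | Both active arms v placebo (16 v 4) |
|---|---|---|
| 0.10 | 0.184 | 0.168 |
| 0.25 | 0.265 | 0.242 |
| 0.50 | 0.306 | 0.280 |
| 0.75 | 0.265 | 0.242 |

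For example, at *p* = 0.50 and 8 v 4: √(0.25 × 0.375) = 0.306. Multiplying by *s* gives the noise that feeding state adds to an informal comparison with placebo.

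**4. Glucose grading**

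Appendix 2 has two scales: fasting Grade 1 is 100–110 and Grade 2 is 111–125 mg/dL; random Grade 1 is 110–125 and Grade 2 is 126–200 mg/dL. So 105 mg/dL is Grade 1 if fasting and ungraded if random, and 115 mg/dL is Grade 2 if fasting and Grade 1 if random. Protocol 10.5.4 uses this scale for intensity and lists a worsening of grade among the considerations for calling a laboratory change an AE. Without fasting status, the correct scale cannot be identified from the data the protocol describes.

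**The case against.** Much can be said for the plan, and several stronger readings that a reader might infer fail.

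- **That V3 is fed because the dose follows a meal.** The same meal rule applies at V4 to V8. At V3, dosing comes after the baseline procedures, so blood may be drawn before the meal, and the visit may be the day before. A fed baseline is permitted, not required.
- **That iron changes compare fed with fasting samples.** The text does not support this. For serum iron, ferritin, UIBC and TSAT, feeding state is open at both the screening baseline and the 2-hour post-dose samples. Transferrin is matched in timing.
- **That the comparison with placebo is biased.** It is not, in expectation. Placebo follows the same schedule, is tabulated alongside the active arms, and is there to separate drug side-effects from other changes (SAP 1.1).
- **That the artefact amounts to a toxicity grade or more.** The documents give no fed-to-fasting difference. Because Appendix 2 has two scales, a random 120 mg/dL and a fasting 105 mg/dL are both Grade 1. The SAP shift tables use low/normal/high ranges, not grades.
- **That the arrival and dosing rules flatly contradict each other.** A sequence of arriving, drawing blood, eating and dosing an hour later would satisfy both. No such sequence is written, so the passages still need reconciling.

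Two more points stand. Sample collection details are left to a laboratory manual (Protocol 8.1.10) that is not among the documents, and it may contain a feeding rule. Also, not every on-treatment sample is certainly fasting: home and local-laboratory draws during COVID-19 have no feeding rule tied to them. These soften the point but do not remove the asymmetry in the protocol's own visit instructions.

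**Conclusion.** The point holds in a limited form. The protocol sets a feeding condition for on-treatment visits and leaves it open at the visits that supply the glucose and triglyceride baseline. Within-arm changes and shift tables for these feeding-sensitive analytes can therefore include a change in feeding state. Its size cannot be stated from the documents; it scales with the unknown share of subjects fed at baseline.

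The contrast with placebo is not systematically affected. With about 4 adult placebo subjects at the planned minimum, though, the chance imbalance in feeding state (SD 0.17 to 0.31, share fed assumed 0.10 to 0.75) makes the artefact hard to subtract by eye. For the iron markers the finding is only that feeding state is not fixed.

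The conclusion assumes that the laboratory manual adds no feeding rule for V1 and V3, and that V4 to V8 chemistry is generally drawn soon after arrival. It concerns a few analytes in a large safety panel, but they belong to the primary endpoint and the remedy is cheap.

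**What to change.** 1. In Protocol 9.1.1.1 and 9.1.2, apply to the V1 and V3 safety-chemistry draws the same pre-sampling feeding condition as at V4 to V8, and align the laboratory manual.
2. Add fasting status and time of last meal to the eCRF at every draw, so that the glucose scale in Appendix 2 can be chosen correctly.
3. For baseline samples already taken, classify each as fasting, non-fasting or unknown from source records where available, and carry that flag into the glucose and triglyceride tables and listings.
4. Reconcile Protocol 9.1.4 (empty-stomach arrival) with the Synopsis for V4 to V8 and Sections 6.4.2.1 and 6.4.2.2 (dose about an hour after meals). This review takes no position on which rule should govern the dose.

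The cost is protocol and manual wording, a small eCRF addition, and subjects having to fast before the V1 and V3 draws. Some earlier samples will probably remain unknown.
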